## 2. CHANGES TO EXISTING SAP

### 2.1 Change 1

#### 2.1.1 Original Text

Section 2.3 Estimand

Analysis Approach:

The difference between treatment arms in the average change from Baseline of the CDR-SB score will be estimated from a linear mixed effects model, including treatment group, time in weeks, and treatment by time interaction as fixed effects; stratification factors (with and without cholinesterase inhibitor therapy), sex and baseline value as covariates. The random effect is on the subject term.

#### 2.1.2 New Text

Section 2.3 Estimand

Analysis Approach:

The difference between treatment arms in the average change from Baseline of the CDR-SB score will be estimated from a linear mixed effects model, including treatment group, and time in weeks as fixed effects; stratification factors (with and without cholinesterase inhibitor therapy), sex and baseline value as covariates. The random effect is on the subject term.

### 2.2 Change 2

#### 2.2.1 Original Text

Section 5.10.2.1 Primary Analysis

The difference between neflamapimod and placebo in the average change from baseline in CDR-SB score during the double-blind treatment phase (i.e., utilizing data from week 8, 12 and 16 in the model) will be estimated using a linear mixed effects model including treatment, time (in weeks), treatment-by-time interaction as fixed effects, cholinesterase inhibitor therapy (Yes/No), age, sex and baseline value as covariates.

QMD Ref: Worldwide-TMP-ST-056-2.0_Effective: 12Aug2025	Governing QMD: Worldwide-SOP-ST-026
Confidentiality Statement	
This document is the property of Worldwide Clinical Trials Inc. and may not be duplicated, copied, altered, or removed from company without prior approval from Worldwide Quality Assurance or in compliance with Worldwide Quality Management Documents.	

Worldwide Clinical Trials Controlled Quality Management Document		
 Worldwide Clinical Trials	Sponsor:	EIP Pharma, Inc.
	Protocol Number:	EIP21-NFD-504
POST DATABASE LOCK STATISTICAL ANALYSIS PLAN ADDENDUM		

## 2.2.2 New Text

### Section 5.10.2.1 Primary Analysis

The difference between neflamapimod and placebo in the average change from baseline in CDR-SB score during the double-blind treatment phase (i.e., utilizing data from week 8, 12 and 16 in the model) will be estimated using a linear mixed effects model including treatment, time (in weeks) as fixed effects, cholinesterase inhibitor therapy (Yes/No), age, sex and baseline value as covariates.

## 2.3 Change 3

### 2.3.1 Original Text

#### Section 5.10.2.1 Primary Analysis

##### Example SAS code:

```
proc mixed data=  method = REML alpha=0.05;
  class <subject> <treatment> <cholinesterase inhibitor therapy> <sex>;
  model <change from baseline> = <treatment> < cholinesterase inhibitor therapy> <sex> <age> <
  baseline value> <time in weeks><treatment>*<time in weeks> / ddfm=kr s;
  random <time in weeks> / subject=<subject> type=un;
  lsmeans <treatment> / cl diff;
run;
```

### 2.3.1 New Text

#### Section 5.10.2.1 Primary Analysis

##### Example SAS code:

```
proc mixed data=  method = REML alpha=0.05;
  class <subject> <treatment> <cholinesterase inhibitor therapy> <sex>;
  model <change from baseline> = <treatment> < cholinesterase inhibitor therapy> <sex> <age> <
  baseline value> <time in weeks> / ddfm=kr s;
  random <time in weeks> / subject=<subject> type=un;
  lsmeans <treatment> / cl diff;
run;
```

## 2.4 Change 4

### 2.4.1 Original Text

#### Section 5.10.2.2 Sensitivity Analysis

##### Example SAS code:

```
proc mixed data=  method = REML alpha=0.05;
  class <subject> <treatment> <cholinesterase inhibitor therapy> <sex>;
  model <change from baseline> = <treatment> < cholinesterase inhibitor therapy> <sex> <age> <
  baseline value> <time in weeks><treatment>*<time in weeks> / ddfm=kr s;
  random <time in weeks> / subject=<subject> type=un;
```

##### Confidentiality Statement

This document is the property of Worldwide Clinical Trials Inc. and may not be duplicated, copied, altered, or removed from company without prior approval from Worldwide Quality Assurance or in compliance with Worldwide Quality Management Documents.

Worldwide Clinical Trials Controlled Quality Management Document		
 Worldwide Clinical Trials	Sponsor:	EIP Pharma, Inc.
	Protocol Number:	EIP21-NFD-504
POST DATABASE LOCK STATISTICAL ANALYSIS PLAN ADDENDUM		

lsmeans <treatment> / cl diff;  
**run;**

#### 2.4.2 New Text

##### Section 5.10.2.2 Sensitivity Analysis

Example SAS code:

```
proc mixed data=  method = REML alpha=0.05;
  class <subject> <treatment> <cholinesterase inhibitor therapy> <sex>;
  model <change from baseline> = <treatment> < cholinesterase inhibitor therapy> <sex> <age> <
baseline value> <time in weeks> / ddfm=kr s;
  random <time in weeks> / subject=<subject> type=un;
  lsmeans <treatment> / cl diff;
run;
```

### 3. ADDITIONS TO EXISTING SAP

#### 3.1 Addition 1

##### 3.1.1 New Text

###### 5.2.9.1 Missing Date of Last Dose of Study Drug

In case the last dose date is missing for a subject, the date of last scheduled visit completed will be used as last dose date.

#### 3.2 Addition 2

Following additional tables are added to the analysis

Table Number	Table Title	Validation Method	Shell Number (if repeat)
Items in bold are not table titles but references to the section headings within eCTD.			
14.2	Efficacy Data		
14.2.1	Primary Efficacy Endpoint		
14.2.1.1c	Primary Endpoint, Clinical Dementia Rating Scale-Sum of Boxes (Descriptive statistics), pTau181 <21 at Screening - Double-Blind Treatment Phase - mITT Analysis Set	Stat IPS	14.2.1.1a
14.2.1.2b	Primary Endpoint, Clinical Dementia Rating Scale-Sum of Boxes (Linear Mixed Effects	Stat IP	14.2.1.2

QMD Ref: Worldwide-TMP-ST-056-2.0_Effective: 12Aug2025	Governing QMD: Worldwide-SOP-ST-026
Confidentiality Statement This document is the property of Worldwide Clinical Trials Inc. and may not be duplicated, copied, altered, or removed from company without prior approval from Worldwide Quality Assurance or in compliance with Worldwide Quality Management Documents.	

**POST DATABASE LOCK STATISTICAL ANALYSIS PLAN ADDENDUM**

Table Number	Table Title	Validation Method	Shell Number (if repeat)
	Model), pTau181 <21 at Screening - Double-Blind Treatment Phase – mITT Analysis Set		
14.2.2	Secondary Efficacy Endpoints		
14.2.2.1.1c	Secondary Endpoint, Change in Timed Up and Go Test (Descriptive Statistics), pTau181 <21 at Screening - Double-Blind Treatment Phase - mITT Analysis Set	Stat IP	14.2.2.1.1a
14.2.2.1.2b	Secondary Endpoint, Change in Timed Up and Go Test (Linear Mixed Effects Model), pTau181 <21 at Screening - Double-Blind Treatment Phase - mITT Analysis Set	Stat IP	14.2.2.1.2
14.2.2.2.2c	Secondary Endpoint, Composite Score of Neuropsychological Test Battery (Descriptive Statistic), pTau181 <21 at Screening - Double-Blind Treatment Phase – mITT Analysis Set	Stat IP	14.2.2.2.2a
14.2.2.2.3b	Secondary Endpoint, Composite Score of Neuropsychological Test Battery (Linear Mixed Effects Model), pTau181 <21 at Screening - Double-Blind Treatment Phase - mITT Analysis Set	Stat IP	14.2.2.2.3
14.2.2.3.1c	Secondary Endpoint, Alzheimer's Disease Cooperative Study Clinical Global Impression of Change (Descriptive Statistics), pTau181 <21 at Screening - Double-Blind Treatment Phase - mITT Analysis Set	Stat IP	14.2.2.3.1a
14.2.2.3.2b	Secondary Endpoint, Alzheimer's Disease Cooperative Study Clinical Global Impression of Change (Mann Whitney U Test), pTau181 <21 at Screening - Double-Blind Treatment Phase - mITT Analysis Set	Stat IP	14.2.2.3.2

QMD Ref: Worldwide-TMP-ST-056-2.0\_Effective: 12Aug2025

Governing QMD: Worldwide-SOP-ST-026

## **Approach for OLE Analysis**

### **Treatment groups:**

There are five treatment groups in the OLE:

Group 1 = old batch for all of OLE (or through ET), N=20

Group 2 = started OLE on old batch, switched at W16 OLE, N=35

Group 3 = started OLE on old batch, switched at W8 OLE, N=26

Group 4 = started OLE on old batch, switched at W4 OLE, N=22

Group 5 = new batch for all of OLE (or through ET), N=46

Total=149, though not all the participants above will be in the mITT analysis, with some being excluded because they do not have at least one efficacy evaluation during the OLE.

In addition, three populations will be evaluated:

1. All participants in OLE
2. OLE participants with screening plasma ptau181 <25.2 pg/mL (2.2 pg/mL in prior version of assay)
3. OLE participants with screening plasma ptau181 < 21 pg/mL (1.8 pg/mL in prior version of assay)

For OLE week 8 data point, groups 1, 2 and 3 will be pooled under “old capsule treatment” and only group 5 will be included under “new capsule treatment” (i.e. only participants with  $\geq 8$  weeks of new capsules will be included).

For the week 16 OLE analysis, groups 1 and 2 will be pooled under the label of “Old Capsules Treatment”, and groups 3, 4 and 5 will be pooled under the label of “New Capsule Treatment” (i.e. all participants with  $\geq 8$  weeks of new capsules will be included for the new capsule treatment group).

The baseline value for all change analyses will be the value at the end of the double-blind period, i.e. at week 16 of the main study (if no value, week 12 will be carried forward).

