### 5.1.3 Modified Intent-To-Treat Analysis Sets

The Modified Intent-To-Treat (mITT) Analysis Set for the double-blind treatment phase includes all subjects who are randomized and received at least one dose of study drug and who have at least one post-dose cognitive assessment (CDR-SB and/or NTB).

The mITT Analysis Set for the open-label extension phase will include all subjects included in the mITT Analysis Set for the double-blind treatment phase who completed the double-blind treatment phase and continued into the open-label extension phase.

Subjects will be analyzed according to the study treatment arm to which they were randomized. The mITT Analysis Set will be used for efficacy analysis. For outputs corresponding to each treatment phase, the analysis set defined for that corresponding phase will be used.

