### **Analyses to be Conducted**

The primary analyses to be conducted are a comparison of new capsule treatment with old capsule treatment:

- For CGIC, this comparison will be a static, unpaired comparison at week 8 using a parametric test (Mann-Whitney U-test).

- For all other endpoints (CDR-SB, TUG, NPI-10, NTB composite, ISLT immediate, ISLT recognition, UPDRS Motor (Part III), the statistical analysis will be change from baseline using linear mixed effects model with baseline as a covariate, i.e. utilizing data from week 8 and 16 of the OLE. The recommendation would be to utilize the LME model from AscenD-LB (phase 2a), but the Worldwide model from RewinD-LB may also be utilized. In addition, descriptive data (i.e. mean, with sem, change from baseline) with p-values (parametric or non-parametric, as appropriate) for the comparison at each of week 8 and 16 will be provided.

A secondary analysis will be comparing the outcomes during the OLE with outcome during the double-blind period in participants who received placebo during the main study and received  $\geq 8$  weeks of new capsules in the OLE (i.e. received new capsules for either the entire 16 weeks or for 12 weeks starting at week 4):

- For CGIC, the comparison will be a paired comparison of the CGIC score at week 16 of the double-blind period with the CGIC score at week 8 of the OLE utilizing Mann-Whitney U-test.
- For all other endpoints, it will be paired comparison (parametric or non-parametric, as appropriate) of the change from baseline to week 8, and from baseline to week 16. If LME model allows for a within-subject comparison, this would be the preferred method.

Finally, comparison of proportions of progressors (early treatment discontinuation or increase from baseline in CDR-SB of  $\geq 1.5$ ) during the OLE with new capsule treatment vs. old capsule treatment will be conducted. Along with proportion of progressors anytime during the OLE, a Kaplan-Meier analysis of the time to progression may be conducted.

All analyses will be conducted with the observed data at each time point. That is, missing data will not be imputed (e.g., week 8 results being carried forward for missing week 16 data).

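### The OLE plan's mITT definition conflicts with Section 5.1.3 and, if applied to the progressor comparison, removes participants who are progressors by definition

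*SAP*

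**What the plan says.** SAP Section 5.1.3 defines the set in two clauses: "The mITT Analysis Set for the open-label extension phase will include all subjects included in the mITT Analysis Set" for the double-blind phase, limited to those "who completed the double-blind treatment phase and continued into the open-label extension phase". Neither clause asks for an assessment during the OLE. The same section states that "The mITT Analysis Set will be used for efficacy analysis", using the set defined for the phase in question.

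The Approach for OLE Analysis, under Treatment groups, gives five groups and then says "Total=149, though not all the participants above will be in the mITT analysis", some being "excluded because they do not have at least one efficacy evaluation during the OLE". The number excluded is not given, overall or by group. The same part lists three populations to be evaluated: all OLE participants, and two subsets defined by screening ptau181.

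Under Analyses to be Conducted, the OLE plan ends with a "comparison of proportions of progressors (early treatment discontinuation or increase from baseline in CDR-SB of" 1.5 or more, new v old capsules, at any time during the OLE. A Kaplan-Meier analysis of time to progression is optional. No analysis set and no capsule grouping is named for either.

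Table 2 of Section 5.2.4 maps an early-withdrawal efficacy assessment on Day 2 to Day 61 of the OLE to Week 8, the first OLE visit listed for the efficacy scales. The changes listed in the post-lock addendum do not touch Section 5.1.3.

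**The concern.** Two definitions of one named set cannot both be programmed. For change scores the difference hardly matters, because a participant with no OLE value contributes nothing under either definition.

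The progressor endpoint is different. Discontinuation alone makes a participant a progressor, so no CDR-SB value is needed to classify that person. Someone who stops before Week 8 and has no withdrawal assessment is a known event, yet fails the OLE plan's condition for mITT. Applying that condition would select on something that happens after OLE entry and is tied to the outcome being counted.

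At stake are the progressor proportions, the early part of any Kaplan-Meier curve, and the new v old contrast if such departures are unevenly spread.

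**Working it through.** **1. Group sizes.** Group 1 is "Group 1 = old batch for all of OLE (or through ET), N=20" and Group 2 is "Group 2 = started OLE on old batch, switched at W16 OLE, N=35". Groups 3, 4 and 5 have 26, 22 and 46. The sum 20 + 35 + 26 + 22 + 46 = 149 reproduces the plan's total.

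**2. Poolings the plan states.**
- Week 8: old = 20 + 35 + 26 = 81, new = 46, with Group 4 (22) left out.
- Week 16: old = 20 + 35 = 55, new = 26 + 22 + 46 = 94.

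**3. Denominator under Section 5.1.3.** It is at most 149, less anyone outside the double-blind mITT set or not a double-blind completer (number not given). Nobody is removed for lack of an OLE evaluation.

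**4. Who is at risk of removal.** Only a participant with no OLE efficacy assessment at all. Groups 2 and 3 switched at OLE Week 16 and Week 8, so they were still on treatment at the first efficacy visit. Losses should therefore fall mainly in Groups 1 and 5, both described as running through early termination, and in Group 4 between Weeks 4 and 8. They need not be balanced between capsules.

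**5. Effect of removal.** With e progressors among n, removing k who are all progressors changes e/n to (e − k)/(n − k). The fall is k(n − e) / [n(n − k)], which is positive whenever e < n. For e = 24, n = 81, k = 5 it is 5 × 57 / (81 × 76) = 4.6 points. For e = 7, n = 46, k = 5 it is 5 × 39 / (46 × 41) = 10.3 points.

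**6. Illustration on the plan's own poolings.** Event counts and removals are assumptions; p is from Fisher's exact test.

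| Pooling | Removed (old, new) | Old | New | p |
|---|---|---|---|---|
| Week 8 | 0, 0 | 24/81 = 29.6% | 7/46 = 15.2% | 0.087 |
| Week 8 | 2, 2 | 22/79 = 27.8% | 5/44 = 11.4% | 0.041 |
| Week 8 | 5, 0 | 19/76 = 25.0% | 7/46 = 15.2% | 0.256 |
| Week 8 | 0, 5 | 24/81 = 29.6% | 2/41 = 4.9% | 0.001 |
| Week 16 | 0, 0 | 16/55 = 29.1% | 14/94 = 14.9% | 0.056 |
| Week 16 | 5, 0 | 11/50 = 22.0% | 14/94 = 14.9% | 0.356 |
| Week 16 | 0, 5 | 16/55 = 29.1% | 9/89 = 10.1% | 0.006 |

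With nearly equal assumed rates the movement is smaller. At Week 8, 24/81 v 14/46 (p = 1.000) becomes 25.0% v 30.4% (p = 0.534) if five are removed from old, or 29.6% v 22.0% (p = 0.398) if five are removed from new.

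**7. Capsule assignment.** The Week 16 pooling counts Groups 3 and 4 as new: 26 + 22 = 48 of the 94. They had to remain to Week 8 or Week 4 to be so classified. A participant who started on old capsules and left before switching is in Group 1, hence old. Restoring early discontinuers under this pooling would add certain events to old and none to those 48.

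**The case against.** A reader might infer that the plan definitely drops the earliest discontinuers from the progressor comparison. The documents do not support that, for two reasons.

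- **No set is named.** The exclusion sentence concerns the mITT analysis, and the first listed population is all participants in the OLE. Counting discontinuation as an event also suits an all-participants denominator. On the other side, the other two listed populations are ptau181 subsets, so the first may mean only that no ptau181 limit applies, and Section 5.1.3 sends efficacy analyses to mITT. Both readings are open.
- **Not every early discontinuer would be lost.** One with a withdrawal efficacy assessment has an OLE evaluation, mapped to Week 8, and stays in.

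It can also be said that this is a secondary matter. The OLE plan's primary analyses are change scores and CGIC, where the exclusion is harmless, and the Kaplan-Meier analysis is optional. That stands and limits the weight of the point.

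The plan's observed-data rule is no defence of the exclusion, because discontinuation is itself observed and counting it imputes nothing.

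**Conclusion.** The conflict between Section 5.1.3 and the OLE plan is plain in the text and needs no assumption. The loss of known progressors is conditional: it occurs if the progressor comparison uses the OLE plan's mITT set and if some participants left with no OLE efficacy assessment. In that case the proportion falls in every affected group (unless all its members progressed), a Kaplan-Meier curve loses early events, and the new v old contrast can be distorted.

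Neither size nor direction can be determined, because exclusions per group are not given. The table shows only that, with groups of this size, two to five removals can matter. A reader might infer a bias towards the new capsules; the same scenarios run the other way when the losses fall on old.

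This should be corrected, but it concerns a supporting comparison in an open-label extension and leaves the change-score analyses untouched.

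**What to change.** 1. Reconcile the two OLE mITT definitions, so that the set name has one meaning throughout.
2. State that the progressor proportion and any Kaplan-Meier analysis include all OLE participants who meet Section 5.1.3, with or without an OLE efficacy evaluation, and that discontinuation is an event at its date.
3. For this analysis, assign capsule group by the batch at OLE start, or treat the switch as a time-varying exposure, so that early discontinuers are not credited to old merely because they left before switching.
4. Keep the condition of at least one OLE efficacy evaluation for the change-score and CGIC analyses only.
5. Report the number without an OLE efficacy evaluation in each of the five groups.

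The cost is a few sentences. Section 5.4 already provides for summaries and listings of early termination in the OLE, so no new data are needed. Reported progressor rates may rise slightly. Grouping by starting batch gives at most 20 + 35 + 26 + 22 = 103 old v 46 new and attributes events after a switch to old, which dilutes a capsule effect; the time-varying option avoids that at the price of a somewhat more complex model.

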### **Analyses to be Conducted**

The primary analyses to be conducted are a comparison of new capsule treatment with old capsule treatment:

- For CGIC, this comparison will be a static, unpaired comparison at week 8 using a parametric test (Mann-Whitney U-test).

- For all other endpoints (CDR-SB, TUG, NPI-10, NTB composite, ISLT immediate, ISLT recognition, UPDRS Motor (Part III), the statistical analysis will be change from baseline using linear mixed effects model with baseline as a covariate, i.e. utilizing data from week 8 and 16 of the OLE. The recommendation would be to utilize the LME model from AscenD-LB (phase 2a), but the Worldwide model from RewinD-LB may also be utilized. In addition, descriptive data (i.e. mean, with sem, change from baseline) with p-values (parametric or non-parametric, as appropriate) for the comparison at each of week 8 and 16 will be provided.

A secondary analysis will be comparing the outcomes during the OLE with outcome during the double-blind period in participants who received placebo during the main study and received  $\geq 8$  weeks of new capsules in the OLE (i.e. received new capsules for either the entire 16 weeks or for 12 weeks starting at week 4):

- For CGIC, the comparison will be a paired comparison of the CGIC score at week 16 of the double-blind period with the CGIC score at week 8 of the OLE utilizing Mann-Whitney U-test.
- For all other endpoints, it will be paired comparison (parametric or non-parametric, as appropriate) of the change from baseline to week 8, and from baseline to week 16. If LME model allows for a within-subject comparison, this would be the preferred method.

Finally, comparison of proportions of progressors (early treatment discontinuation or increase from baseline in CDR-SB of  $\geq 1.5$ ) during the OLE with new capsule treatment vs. old capsule treatment will be conducted. Along with proportion of progressors anytime during the OLE, a Kaplan-Meier analysis of the time to progression may be conducted.

All analyses will be conducted with the observed data at each time point. That is, missing data will not be imputed (e.g., week 8 results being carried forward for missing week 16 data).

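### The OLE capsule comparison tests CGIC unadjusted between batch groups with no described randomisation, and the plan does not say what the rating is anchored to

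*SAP*

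**What the plan says.** The Approach for OLE Analysis names new versus old capsules as the primary OLE comparison. For the clinician's global rating it specifies: "For CGIC, this comparison will be a static, unpaired comparison at week 8 using a parametric test (Mann-Whitney U-test"). No covariate is mentioned.

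For CDR-SB, TUG, NPI-10, the NTB composite, the two ISLT scores and UPDRS Part III, the same section says "the statistical analysis will be change from baseline using linear mixed effects model with baseline as a covariate". Under *Treatment groups* it adds: "The baseline value for all change analyses will be the value at the end of the double-blind period", with Week 12 carried forward if Week 16 is missing.

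The comparison groups come from the batch taken and the time of switch. At OLE Week 8, "groups 1, 2 and 3 will be pooled under “old capsule treatment” and only group 5 will be included under “new capsule treatment". The old pool is made up of "Group 1 = old batch for all of OLE (or through ET), N=20"; "Group 2 = started OLE on old batch, switched at W16 OLE, N=35"; and "Group 3 = started OLE on old batch, switched at W8 OLE, N=26". The remaining switchers ("Group 4 = started OLE on old batch, switched at W4 OLE, N=22") are left out at Week 8. Nothing in the section describes random allocation to batch.

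Section 5.2.17 defines the ADCS-CGIC as a seven-point rating of change: 1 is marked improvement, 4 no change and 7 marked worsening. The OLE plan does not say whether the OLE rating is made against OLE entry or against main-study baseline.

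**The concern.** An unadjusted rank test asks whether two groups have the same distribution of ratings. Between randomised arms, a difference can be put down to treatment or chance. Here the groups differ by which batch people received and when they switched, so they may already have differed when the OLE began. OLE participants also come from both randomised arms, and the plan does not say how prior arm is distributed over the batch groups.

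If the CGIC is still rated against main-study baseline, the OLE Week 8 rating includes the 16 double-blind weeks, before any OLE capsule was taken. A difference already present at entry could then be read as a capsule effect, or could hide one. The listed mixed-model endpoints have at least a stated adjustment for this, and CGIC has none. A useful covariate exists: the secondary OLE analysis already uses the double-blind Week 16 CGIC.

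Separately, the Mann-Whitney test is non-parametric. Calling it parametric is an error of wording, but it leaves a programmer two conflicting descriptions of the test.

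**Working it through.** **Inputs from the SAP.** OLE groups 1 to 5 have 20, 35, 26, 22 and 46 participants. Section 5.10.1 gives a two-sided 5% level as the general rule; the OLE text states none.

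**The plan's own figure.** 20 + 35 + 26 + 22 + 46 = 149, which matches the stated total.

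**Week 8 contrast.** Old = 20 + 35 + 26 = 81. New = 46. Not used = 149 − 81 − 46 = 22. These are upper limits, because the plan says some participants will be excluded for lack of an OLE efficacy evaluation.

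**Assumptions (the SAP gives no values).** ρ is the correlation between status at OLE entry and the Week 8 rating; δ is the entry difference between the groups in SD units. I took ρ from 0 to 0.7 and δ of 0, 0.2 and 0.4.

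**Bias with no capsule effect.** An entry difference δ shifts the Week 8 mean by ρδ. For δ = 0.4 the shift is 0.12, 0.20 and 0.28 SD at ρ = 0.3, 0.5 and 0.7. The standard error in SD units is √(1/81 + 1/46) = √0.0341 = 0.185. The shift is therefore about 0.65, 1.08 and 1.52 standard errors, and a two-sided 5% normal test would reject in about 10%, 19% and 33% of trials.

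A simulation put this on the actual type of scale: 3,000 trials per setting, latent normal values cut into seven categories. It compared the Mann-Whitney test with a rank ANCOVA on the entry rating.

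| ρ | δ | Mann-Whitney | Rank ANCOVA |
|---|---|---|---|
| 0 | 0.4 | 4.4% | 4.5% |
| 0.3 | 0.2 | 5.9% | 4.5% |
| 0.3 | 0.4 | 8.5% | 4.7% |
| 0.5 | 0.2 | 8.3% | 4.8% |
| 0.5 | 0.4 | 17.1% | 4.9% |
| 0.7 | 0.2 | 11.4% | 5.6% |
| 0.7 | 0.4 | 31.0% | 5.4% |

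With δ = 0 both tests stay near 5%.

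**Precision.** Adjustment multiplies the variance by 1 − ρ²: 0.91, 0.75 and 0.51 at ρ = 0.3, 0.5 and 0.7. The detectable difference at 80% power is (1.960 + 0.842) × √[(1 − ρ²)(1/81 + 1/46)].

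- Unadjusted: 2.802 × 0.185 = 0.52 SD, or 0.53 SD after the rank test's efficiency factor of 3/π.
- Adjusted: 0.49, 0.45 and 0.37 SD at ρ = 0.3, 0.5 and 0.7.

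For an assumed 0.5 SD effect with balanced entry, the seven-category simulation gives power of 71% to 74% unadjusted. Adjusted power is 77%, 83% and 91% at ρ = 0.3, 0.5 and 0.7. At ρ = 0 both are 73%.

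**The case against.** The strongest reply is that CGIC already measures change, so it has no baseline value of its own to enter as a covariate, and calling it a raw status score would be wrong. This stands, and it limits the point. If the OLE rating is anchored at OLE entry, the double-blind change is not in the score. The secondary analysis, which pairs the double-blind CGIC with the OLE CGIC alongside changes within each period, fits that reading but does not prove it. The baseline definition in Section 5.2.3 (before first dose of study drug) does not settle it either, because the OLE plan sets its own baseline for change analyses. The anchor may be in the protocol or rater instructions, which I have not seen.

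A reader might infer that CGIC is the only OLE outcome without adjustment. The text does not support that. The per-visit p-values, the progressor proportions, the Kaplan-Meier analysis and the plasma biomarker comparison name no covariate either. The contrast holds only with the endpoints listed for the mixed model.

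A reader might also infer that the groups were in fact unbalanced, or that the false-positive rate is 31%. The SAP gives no entry comparison and no correlation. The near-5% rate for the adjusted test is largely built in, since the simulated imbalance acts only through the covariate adjusted for.

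Finally, Section 5.10.3.3 uses the same unadjusted test in the double-blind phase, and the OLE comparison lies outside the testing hierarchy of Section 5.10.5. The first is no precedent, because randomisation protects the double-blind test. The second limits the consequence, but the OLE plan still calls this comparison primary.

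**Conclusion.** The point holds in a limited form. The plan uses an unadjusted test where no randomisation to batch is described, has a relevant entry rating to hand, and leaves the rating's anchor unstated.

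With a main-study anchor, entry differences enter the comparison, in either direction. With an OLE-entry anchor, what remains is prognostic imbalance and some lost precision, so the effect is likely to be smaller. Under an assumed 0.4 SD imbalance and correlations of 0.3 to 0.7, the false-positive rate is about 8.5% to 31%; at 0.2 SD it is about 6% to 11%. At zero correlation there is neither bias nor gain. The change is worth making because it is cheap. It does not show that any particular OLE result is wrong.

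**What to change.** In *Analyses to be Conducted*:

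1. State whether the OLE CGIC is rated against OLE entry or main-study baseline. Settle this first, since it determines how the entry rating is interpreted.
2. Make the Week 8 CGIC capsule comparison a proportional-odds model (or a rank ANCOVA; name one in advance). Use capsule group as the factor, with double-blind Week 16 CGIC, OLE-baseline CDR-SB and prior randomised arm as covariates. Report the adjusted effect with a 95% confidence interval.
3. Keep the Mann-Whitney test as supportive.
4. Change parametric to non-parametric.

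The cost is a few lines of text and one model, with no new data. Participants without a double-blind Week 16 CGIC drop out of the adjusted model. The Week 12 carry-forward is unlikely to help them, because Table 1 in Section 5.2.4 maps double-blind ADCS-CGIC only to Week 16. The simulation adjusted for the entry rating alone, so its figures illustrate the gain from this model and do not measure it. Confounding by calendar time or site is not removed, and the report should say so.

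### The primary new- versus old-capsule comparison in the open-label extension states no double-blind-arm term or stratum, so it can be confounded if the former-arm mix differs between capsule groups

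*SAP*

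**What the plan says.** The section Approach for OLE Analysis, under Treatment groups, defines five groups by capsule batch and week of switch. Group 1 (20 participants) stayed on old capsules throughout. Groups 2, 3 and 4 (35, 26 and 22 participants) began on old capsules and changed at OLE Weeks 16, 8 and 4 respectively. The last group is given as "Group 5 = new batch for all of OLE (or through ET), N=46".

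At Week 8, groups 1 to 3 form the old-capsule pool and group 5 the new-capsule pool. At Week 16, groups 1 and 2 are old and groups 3 to 5 are new. The double-blind arm plays no part in either pooling. On the starting point, the text says: "The baseline value for all change analyses will be the value at the end of the double-blind period".

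Under Analyses to be Conducted, new against old capsules is the primary OLE comparison. For CGIC, "this comparison will be a static, unpaired comparison at week 8", by a Mann-Whitney test with no stratum. For the other endpoints it is "change from baseline using linear mixed effects model with baseline as a covariate". The text then recommends the phase 2a mixed model, whose terms the document does not list, and also allows the Worldwide model. In the addendum's revision of Section 5.10.2.1, the Worldwide model has treatment, time, cholinesterase inhibitor use, age, sex and baseline. Treatment there is the randomised arm. The OLE text does not say whether that term becomes capsule type; if it does, the arm drops out.

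**The concern.** The OLE baseline is measured after 16 weeks of placebo or of neflamapimod. From the same Week 16 score, a former-placebo participant starts active drug, while a former-neflamapimod participant continues it or changes batch. Their expected change can differ, and the score does not show which situation applies. Adjusting for baseline therefore does not stand in for the arm.

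No randomisation of capsule group is described, and the number of former-placebo participants in each group is not given. If the two pools differ in that share, and OLE change differs by former arm, part of the arm difference is counted as a capsule effect. If the shares are equal, the unmodelled arm difference only adds residual variance.

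**Working it through.** **Inputs from the SAP.** Group sizes 20, 35, 26, 22 and 46 (Treatment groups). A difference of -0.56 and Cohen's d of 0.70 (Section 3), used only to set a scale; they come from the phase 2a analysis restricted to patients without Alzheimer's co-pathology.

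**Assumptions, not in the SAP.** The difference in OLE change between former arms, delta, is taken as 0.25, 0.56 or 1.0 CDR-SB points. The residual SD is 0.56 / 0.70 = 0.80. The counts are those before mITT exclusions.

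**1. Group sizes.** 20 + 35 + 26 + 22 + 46 = 149, as the SAP states. The Week 8 pools are 20 + 35 + 26 = 81 old and 46 new. The Week 16 pools are 20 + 35 = 55 old and 26 + 22 + 46 = 94 new.

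**2. Chance gap in arm mix.** If each participant is equally likely to come from either arm, the SE of the difference in former-arm share is 0.5 × sqrt(1/n_old + 1/n_new).

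- Week 8: 0.5 × sqrt(1/81 + 1/46) = 0.092; 95% limit 1.96 × 0.092 = 0.18.
- Week 16: 0.5 × sqrt(1/55 + 1/94) = 0.085; 95% limit 1.96 × 0.085 = 0.17.
- The mean absolute gap is about 0.8 × SE, or 7 percentage points at either visit.

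**3. Shift in the capsule estimate for a given gap.** Without an arm term, shift = gap × delta. The SE of the capsule contrast at Week 8 is 0.80 × sqrt(1/81 + 1/46) = 0.148.

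| Assumed delta | Week 8 shift at the 18-point limit | In SEs (0.148) |
|---|---|---|
| 0.25 | 0.05 | 0.31 |
| 0.56 | 0.10 | 0.69 |
| 1.0 | 0.18 | 1.22 |

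At a typical gap of 7 points with delta 0.56, the shift is 0.07 × 0.56 = 0.04. At Week 16 the limit gives 0.166 × 0.56 = 0.09.

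**4. Simulation.** Ordinary regression at Week 8 (81 v 46), no true capsule effect, delta 0.56, SD 0.80, 4,000 runs per scenario. This is a single-visit simplification of the mixed model.

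| Arm mix | Rejection without arm term | Rejection with arm term |
|---|---|---|
| Fixed gap 0 | 3.9% | 5.4% |
| Fixed gap 10 points | 5.3% | 5.6% |
| Fixed gap 20 points | 10.3% | 5.0% |
| Fixed gap 30 points | 17.9% | 4.7% |
| Random, equal chance | 4.7% | 4.9% |

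With the arm term the mean estimate is about 0 throughout. In the random-mix row the mean estimate is about 0 without it too; the SD of the estimate is 0.155 without and 0.147 with the term, a ratio of 1.05.

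**The case against.** Several stronger readings are tempting, and the document does not support them.

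- *The model adjusts for the baseline score and nothing else.* Baseline is the only covariate the OLE text names, but the Worldwide model carries more and the phase 2a terms are not shown. What can be said is that no arm term or stratum is stated.
- *Carry-over is in the capsule estimate.* That needs an unequal arm mix, which is not reported. Double-blind allocation was 1:1 and randomised (Section 4), so the expected gap is near zero unless OLE entry or batch timing differed by arm. Nothing shows that it did.
- *Stock arrival decided who got which capsule.* The text gives batch and switch week, not the reason for them.
- *Gaps of 17 to 18 points should be expected.* Those are 95% limits. They rest on the same equal-chance assumption under which the unadjusted estimate is unbiased on average and chance imbalance is covered by its SE.

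The SAP also does not ignore the arm elsewhere. Section 5.3 keeps OLE summaries under the double-blind group. The secondary OLE analysis isolates former-placebo participants given new capsules, and the within-subject biomarker comparison in former-placebo participants separates old from new capsules. None of these is an arm-adjusted comparison of new with old capsules.

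What stands is that, in a comparison with no described randomisation, a known variable that may predict the outcome is left out. The realised gap in this trial is a fixed, countable number, and it can be adjusted for directly.

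**Conclusion.** The point holds as a gap in specification with a conditional risk. It is not a demonstrated bias. If the arm mix is equal, the cost is about 5% in SE, assuming a former-arm difference of 0.56 and SD 0.80. If the mix happens to lie at its 95% chance limit, the Week 8 CDR-SB estimate moves by 0.05 to 0.18 points across the assumed differences of 0.25 to 1.0. A systematic gap could be larger, and the document gives no means to judge whether one exists. Chance gaps are wider in the two pTau181-restricted populations wherever these are smaller than the full OLE group. The size of any former-arm difference and the arm mix are assumptions throughout.

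**What to change.** - Include double-blind arm (placebo or neflamapimod) as a fixed effect alongside capsule group in whichever OLE mixed model is used, and state that both terms are present. If the Worldwide model is chosen, say what its treatment term denotes in the OLE.
- For CGIC, replace the unstratified rank test with a van Elteren test stratified by double-blind arm.
- Tabulate double-blind arm by capsule group, so that readers can see the realised mix.
- Report the new-minus-old difference by former arm descriptively only. An even split leaves 46 / 2 = 23 new-capsule participants per arm at Week 8. The SE within one arm would then be about 0.80 × sqrt(1/40.5 + 1/23) = 0.21, against 0.148 for the pooled contrast.

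The cost is one degree of freedom per model, one stratification factor and one table. The randomised arm is on record for every participant, so no new data are needed.
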